3.1.1 TACE guidelines

TACE will be performed per institution standard of care or separate protocol specifications. Documentation of the TACE procedure will be provided to the PI.

3.1.2 FMISO Hypoxia Imaging

Following screening and eligibility determination, patients will be contacted by a research staff member to offer enrollment into the protocol and schedule an appointment for [¹⁸F] FMISO PET-CT scanning. Consented patients are scheduled for [¹⁸F] FMISO PET-CT scanning. If the patient is not an inpatient at NIH CC, they should arrive approximately 1-2 hours before the appointed time for imaging, to go through outpatient admissions, and then to the PET scanning department to sign informed consent. Once imaging is completed, the patient, based on their clinical condition, will return to the inpatient ward, transferred to a day hospital or clinic, or discharged home for further monitoring or instruction.

3.1.3 Post TACE Cross-sectional Imaging for determination of progression despite TACE

Patients will receive CT and MRI of the abdomen with contrast at 4-6 week intervals following TACE to detect tumor progression despite TACE per standard of care. Scanning interval may be increased to 3 months if stable disease is documented on at least two successive imaging studies. If these studies were done outside NIH CC, digital copies will be provided to PI at each post-TACE interval for progression documentation and analysis (Section 3.3)

3.2 DRUG ADMINISTRATION

[¹⁸F] FMISO imaging technique will be adapted from previously reported imaging studies for head and neck malignancies¹⁷ and pancreatic malignancy¹⁸. The [¹⁸F] FMISO will be administered intravenously at a dose of 0.1mCi/kg for hypoxia imaging. PET-CT imaging of the abdomen will be performed 120 minutes after injection. A repeat scan at 240 minutes after injection may be obtained if tumor-to background uptake is suboptimal and only if the patient's condition permits. Each scan requires up to 30 minutes. Based upon previous reports, it is expected that [¹⁸F] FMISO uptake will peak within target liver tumor two hours following intravenous administration. Considerable background activity is expected in normal liver tissue, and techniques to maximize signal-to-noise activity in target tumors may include 1)

characterization of observed focal uptake relative to serum [¹⁸F] FMISO activity, where a tumor: serum ratio >1.2 has been considered indicative of hypoxia, or 2) delayed imaging up to 4 hours post-injection with subtraction techniques to identify focal tumoral uptake.

3.3 IMAGE ANALYSIS

Feasibility of FMISO PET imaging post-TACE will be assessed by individually characterizing FMISO uptake in treated tumors as absent, background (equivalent to normal liver), or increased relative to liver background. Lesions demonstrating any increased activity compared to background liver will be further characterized as diffusely or focally increased activity.

Changes in FMISO PET activity before and following TACE will be descriptively compared and change in peak SUV will be assessed as response to embolization.

Individual liver tumors which demonstrate progression defined by increased size and/or enhancement will be evaluated for geographic FMISO uptake correlation. CT or MRI images demonstrating progression will be registered with FMISO PET-CT images automatically using OncoNav software (developed at the Center of Interventional Oncology) to determine whether qualitatively increased or decreased FMISO uptake is observed in spatial relation to tumor progression.

Increased FMISO activity which correlates positively with tumor progression will be further quantified using calculated standardized uptake values (SUV) or tumor-to- serum activity ratio in manually selected regions of interest (ROI).

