1.2.3 Rationale

The primary hypothesis of this study states that tumor progression post-TACE results from changes in tumor phenotype induced by sublethal treatment-related hypoxia. The goal of the proposed pilot study is to test the feasibility of hypoxia imaging of the liver post-TACE. Early imaging detection of residual hypoxic tumor acutely following TACE may ultimately correspond to undertreated tumor and could be used to optimize TACE outcomes with targeted combinational therapies.

This pilot study will evaluate fifteen patients who will receive TACE therapy for primary or metastatic hepatic malignancy. They will undergo PET imaging of the liver with [¹⁸F] FMISO to: 1) determine the feasibility of hypoxic tumor identification despite relatively high liver background signal, and 2) identify the pattern and distribution of acute post-TACE tumor hypoxia relative to demonstrated tumor progression despite therapy. Patients will be followed according to standard community practice with conventional cross-sectional imaging (CT and/or MRI) to confirm tumor progression. Image fusion analysis will be performed to determine degree of correlation between focal hypoxia and site(s) of progression.

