3 STUDY IMPLEMENTATION

3.1 STUDY DESIGN

Fifteen patients with metastatic or primary hepatic malignancy will be enrolled to yield a minimum of ten evaluable patients. Prior to TACE, all patients will undergo conventional baseline imaging. The first five patients enrolled will receive a single dose of the study imaging agent (FMISO) post-TACE to determine imaging parameters and feasibility. Subsequent to the feasibility study, the remaining patients (#6-15) will receive the hypoxia imaging agent before and following TACE to determine changes in uptake pattern attributable to arterial embolization. Following TACE patients will be monitored according to standard of care until tumor progression is documented. Registration of functional and/or metabolic imaging demonstrating progression with immediate post-TACE hypoxia imaging will be performed for correlative analysis.

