6 DATA COLLECTION AND EVALUATION

6.1 DATA COLLECTION

Data collection for this study will include imaging data used to identify acute post-embolization tumor hypoxia, as well as conventional post-treatment imaging and measurement of tumor markers used to identify tumor progression despite therapy. Other follow up data such as date of death will also be collected. The [¹⁸F] FMISO PET-CT imaging and post-treatment CT and MRI will be stored in PACS prior to image registration and analysis. PET-CT and conventional CT images will be transferred to a workstation for registration analysis. Identifiers will be removed from fused images for characterization of degree of overlap between documented tumor progression and acute post-treatment hypoxia. Imaging data including determination of response by mRECIST criteria as well as tumor marker levels will be collected in an Excel spreadsheet that will be stored in a password-protected PC kept in a secured office.

Grade 2 events and higher will be recorded in the study database. Grade 1 events will not be recorded or reported.

The PI will be responsible for overseeing entry of data into an in-house password protected electronic system and ensuring data accuracy, consistency and timeliness. The principal investigator, associate investigators/research nurses and/or a contracted data manager will assist with the data management efforts. Source data obtained during the conduct of the protocol will be kept in secure network drives or in approved alternative sites that comply with NIH security standards. Primary and final analyzed data will have identifiers so that research data can be attributed to an individual human subject participant.

End of study procedures: Data will be stored according to HHS and FDA regulations as applicable.

Loss or destruction of data: Should we become aware that a major breach in our plan to protect subject confidentiality and trial data has occurred, the IRB will be notified.

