6.2.3 Response Criteria

All of the patients who met the eligibility criteria (with the possible exception of those who could not undergo ¹⁸F-MISO imaging) should be included in the main analysis of the response to the imaging agent. All conclusions should be based on all eligible patients.

For the purposes of this study, patients with baseline CT or MRI and should be re-evaluated for response per standard of care approximately 4 to 6 weeks following TACE treatment with an abdominal CT and MRI. Scanning interval may be increased to 3 months instead of 4-6 weeks if stable disease is documented on at least two successive imaging studies obtained at the 4-6 week post-TACE interval.

Response and progression of only targeted tumors will be evaluated in this study using the revised modified Response Evaluation Criteria in Solid Tumors (mRECIST) guidelines.¹⁹

Complete Response (CR)	Disappearance of any intratumoral arterial enhancement
Partial Response (PR)	At least 30% decrease in the sum of the diameters of viable (enhancement in the arterial phase) target lesions, taking the baseline sum of the diameters of target lesions

Stable Disease (SD)	Any cases that do not qualify for either PR PD
Progressive Disease (PD)	An increase of at least 20% in the sum of the diameters of viable (enhancing) target lesion, taking as reference the smallest sum of the diameters of viable (enhancing) target lesions recorded since treatment started.

European Association for the Study of Liver, European Organization for Research and Treatment of Cancer. Journal of Hepatology, 2012 56:908-943.

Serum alpha-fetoprotein levels will be assessed and compared pre- and post-TACE per standard of care as a marker for tumor progression despite TACE. Cross-sectional and PET imaging will continue to be obtained at 4-6 week intervals until imaging evidence of disease progression is obtained and compared with FMISO imaging.

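### Does the tumor-by-tumor FMISO mapping in Section 3.3 need a measurable progression threshold, a named comparison scan and one agreed image type?

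*Combined protocol and SAP*

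**What the plan says.** Section 3.3 sets the selection rule for the mapping: "Individual liver tumors which demonstrate progression defined by increased size and/or enhancement will be evaluated for geographic FMISO uptake correlation". Section 6.2.3 sets the progression rule for the study: "Response and progression of only targeted tumors will be evaluated in this study using the revised modified Response Evaluation Criteria in Solid Tumors". Its table calls disease progressive when the sum of enhancing target diameters rises at least 20% above the smallest sum recorded, and it counts a fall of at least 30% from the baseline sum as partial response. The same section runs follow-up imaging "until imaging evidence of disease progression is obtained and compared with FMISO imaging".

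The purpose of the mapping is in Section 1.2.3: "Image fusion analysis will be performed to determine degree of correlation between focal hypoxia and site(s) of progression". It is the second of two uses given there for the FMISO scans. The primary objective in Section 1.1.1 covers feasibility and the description of hypoxia patterns soon after TACE, and does not mention progression.

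On the images, Section 3.1 says "Registration of functional and/or metabolic imaging demonstrating progression with immediate post-TACE hypoxia imaging will be performed for correlative analysis", Section 3.3 says "CT or MRI images demonstrating progression will be registered with FMISO PET-CT images automatically", and Section 6.1 says "PET-CT and conventional CT images will be transferred to a workstation for registration analysis". For follow-up, Section 6.2.3 says "Cross-sectional and PET imaging will continue to be obtained at 4-6 week intervals", while the follow-up column of the calendar in Section 3.4 lists CT/MRI and no PET.

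**The concern.** Section 3.3 works tumor by tumor and Section 6.2.3 works on a patient's sum. With several targeted tumors, a sum cannot show which one progressed, and one tumor can grow while the sum falls. The text does not say whether such a tumor is mapped, how much growth or enhancement counts, or whether growth is judged against the pre-TACE scan or the smallest later measurement. Two readers could therefore map different tumors in the same patient.

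Selection also has a knock-on effect: under Section 3.3, the further SUV or tumor-to-serum quantification is reserved for uptake that matches progression. The differing image descriptions could lead one reader to register a CT and another a PET scan. What is at stake is the consistency of a descriptive result in about ten patients.

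**Working it through.** **Inputs from the plan.** Progression: at least +20% in the sum over the smallest sum (6.2.3). Partial response: at least -30% from the baseline sum (6.2.3). Fifteen patients enrolled for at least ten evaluable (3.1). No power or significance calculation (8). The plan gives no figure for the mapping, so there is none to reproduce. Tumor numbers and sizes below are assumed, with no measurement error.

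**1. Sum against single tumor.** Enhancing diameters of 40, 30 and 20 mm become 28, 22 and 30 mm.
- Sum: (28 + 22 + 30)/(40 + 30 + 20) - 1 = 80/90 - 1 = -11.1%.
- Third tumor: 30/20 - 1 = +50%.
- Partial response would need a sum of 0.7 x 90 = 63 mm or less, so 80 mm does not qualify. Progression would need an earlier sum of 80/1.2 = 66.7 mm or less. Without one, this is stable disease.
- If 3.3 stands alone the third tumor is mapped now. If the sum rule comes first it is not mapped at this scan. With the others unchanged and 80 mm as the smallest sum, progression comes at 1.2 x 80 = 96 mm, when the third tumor reaches 96 - 50 = 46 mm. The mapping is then delayed, and lost only if the patient leaves the study first.

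**2. Growth needed in one of k equal tumors, others unchanged.** 20% x k gives 20%, 40% and 60% for k = 1, 2 and 3.

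**3. Two of three 30 mm tumors shrink to 21 mm.**
- Against the pre-TACE sum of 90 mm: (1.2 x 90 - 42)/30 - 1 = 66/30 - 1 = +120%.
- Against a recorded smallest sum of 72 mm: (1.2 x 72 - 42)/30 - 1 = 44.4/30 - 1 = +48%.

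**4. Comparison scan for one tumor.** 30 mm before TACE, 20 mm at its smallest, 26 mm now: 26/30 - 1 = -13.3% against the first and 26/20 - 1 = +30% against the second.

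**5. A single target.** 30 to 35 mm is +16.7%, larger but not progressive by 6.2.3; 30 to 36 mm is +20%, progressive. The gap between sum and lesion disappears, and only the threshold question is left.

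So the rules can differ. The next step is to see what the rest of the plan already settles.

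- **When progression occurs.** Section 6.2.3 applies mRECIST to progression of targeted tumors throughout the study and supplies a threshold and a reference. Section 3.1.3 sends the follow-up scans to Section 3.3 for analysis. The natural reading is that 6.2.3 fixes the time and 3.3 picks the tumors.
- **Which tumors.** Section 6.2.1.3 limits evaluation to measurable lesions targeted by TACE, and Section 6.2.2 has each reported lesion assessed by the same method at baseline and follow-up. Per-lesion measurements will therefore exist.
- **Which images.** Section 1.1.1 registers FMISO uptake with cross-sectional imaging. Sections 1.2.3, 3.1.3, 3.3 and 6.2.1.2 all use CT, MRI or both for follow-up or progression. The sentence in 6.1 that omits MRI follows one that stores CT and MRI ahead of registration, so it is ambiguous and does not conflict. Section 6.2.3 speaks of comparing with FMISO, not registering, and Section 6.2.2 lists PET as an option. Only Section 3.1 clearly departs on the registered image. PET in 6.2.3 against the calendar is a separate scheduling mismatch.
- **What is retained.** Section 3.3 classifies FMISO uptake in treated tumors regardless of progression, and Section 6.1 stores the PET-CT, CT and MRI. A different choice of tumors could be described later from the same images.

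**The case for a change.** The strongest case for a change is that this mapping is one of two stated purposes of the scans, and Section 1.2.3 promises a degree of correlation. A rule without a threshold, applied by readers who can see the FMISO picture, leaves room to favor matches. The choice also decides what is quantified further. Progression ends follow-up under Sections 3.4 and 3.5.2, so a loose definition could affect more than the map. There is even some doubt over what size means: Section 6.2.1.3 builds the baseline sum from longest diameters, while 6.2.3 uses enhancing diameters.

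Part of this stands. Section 3.3 has no measurable threshold, no comparison scan and no cross-reference to 6.2.3, and Section 3.1 is loosely worded on images. But Section 3.3 does give a per-lesion criterion, in qualitative form. The follow-up and off-study wording is not shown to conflict with 6.2.3.

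Asking for a written threshold would not settle much either. The plan offers no basis for choosing one, and the choice is a real trade-off. Putting the sum rule first leaves isolated growth unmapped. Leaving it out maps tumors in patients still classed as stable, some of which may be reading variation. For a first look at whether hypoxia and progression coincide, qualitative reading of each tumor is a defensible choice.

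**Conclusion.** No change is needed. The lack of a threshold and comparison scan is a gap that readers can fill sensibly from Section 6.2.3, and the image wording in Section 3.1 is a clerical slip against several sections that agree on CT or MRI. Whether the sum rule should come before tumor selection is a fair trade-off in a pilot.

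No sample size, error rate or test is affected, since Section 8 has none, and the uptake categories that carry the feasibility assessment do not depend on the mapping. One patient handled differently is 1/10 = 10% of the minimum evaluable set. The share of mapped tumors cannot be worked out, because the plan does not say how many will progress. The disagreements between the rules shown above rest entirely on assumed tumor sizes.

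The conclusion assumes that readers take progression from 6.2.3, that the stored images remain available, and that the report says which tumors were mapped and why. It would be different if a test or a go/no-go decision were attached to the correlation; the plan attaches neither.

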7.5 DATA AND SAFETY MONITORING PLAN

7.5.1 Principal Investigator/Research Team

The clinical research team will meet regularly while patients remain in the study. Any adverse event, toxicity, and imaging evaluations will be discussed as a group.

All data will be collected in a timely manner and reviewed by the principal investigator or a lead associate investigator. Adverse events will be reported as required above. Any safety concerns, new information that might affect either the ethical and or scientific conduct of the trial, or protocol deviations will be immediately reported to the IRB using iRIS and to the Sponsor.

The principal investigator will review adverse event and response data on each patient to ensure safety and data accuracy. The principal investigator will personally conduct or supervise the investigation and provide appropriate delegation of responsibilities to other members of the research staff.

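### The FMISO–progression match is a qualitative call made once the progression site is on the image; nothing requires the FMISO location to be recorded first

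*Combined protocol and SAP*

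**What the plan says.** Three parts of the protocol describe the match.

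- **Purpose.** Section 1.2.3: "Image fusion analysis will be performed to determine degree of correlation between focal hypoxia and site(s) of progression". The Précis and section 3.1 also name the relation of post-TACE hypoxia to later progression as a purpose of the design.
- **Selection and reading.** Section 3.3: "Individual liver tumors which demonstrate progression defined by increased size and/or enhancement will be evaluated for geographic FMISO uptake correlation". Next, "CT or MRI images demonstrating progression will be registered with FMISO PET-CT images automatically using OncoNav software", and the aim of that step is "to determine whether qualitatively increased or decreased FMISO uptake is observed in spatial relation to tumor progression". SUV or tumor-to-serum ratio, in manually chosen regions, follows only where increased uptake has already been found to match progression.
- **Handling of the images.** Section 6.1: "Identifiers will be removed from fused images for characterization of degree of overlap between documented tumor progression and acute post-treatment hypoxia". Section 6.2.3 gives the same order in time: imaging continues "until imaging evidence of disease progression is obtained and compared with FMISO imaging".

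Section 3.3 also has a separate feasibility grade for each treated tumor: no uptake, uptake equal to liver, or uptake above liver, with the last split into diffuse and focal.

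**The concern.** When the steps are followed as written, the progression site is in view when someone decides whether FMISO uptake there is raised or lowered. That decision has no threshold, and closeness in space is not defined. Section 3.2 expects considerable background activity in normal liver, so borderline calls are likely. A reader who expects hypoxia to precede progression can, without intending to, call faint uptake beside a known progression site increased, or accept a looser spatial match there than elsewhere.

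What is at stake is the only analysis that bears on the study hypothesis in 1.2.3. The later SUV or serum-ratio figures cannot correct a biased match, because they are taken only where the match was positive. Nor would more patients help, since this is a reading bias and not a matter of precision.

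**Working it through.** The plan gives no figure for this analysis, so there is none to reproduce. The check sets the sections side by side and asks whether any of them separates the FMISO read from knowledge of the progression site.

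1. **Order of reading (3.3, 6.2.3).** Progression is found first, then images are registered, then uptake is called. Only progressed tumors enter. No step records FMISO location before this.
2. **Removal of identifiers (6.1).** This conceals identity. A fused image still shows progression and uptake together.
3. **Automatic registration (3.3).** This fixes the alignment. The call of increased or decreased remains a visual judgement.
4. **Whole-lesion grade (3.3).** It could be made on the day of the scan, and some early look is implied: the 240-minute repeat in 3.2 depends on tumor-to-background uptake, and the six-patient rule in 3.7 depends on tumor uptake. But the grade says only whether uptake is diffuse or focal, not where it lies, and no section says it is fixed before follow-up.
5. **Quantitative criteria (3.2, 3.3).** A tumor-to-serum ratio above 1.2 appears in 3.2 as one technique that may be used. Section 3.3 does not apply it to the match.
6. **Progression site.** Section 3.3 works tumor by tumor, on size and/or enhancement. Section 6.2.3 defines progressive disease by the sum of diameters over target lesions, which gives no location. The site is therefore a judgement too, and no section says it is marked without PET displayed.
7. **Separation of readers.** FMISO is performed only at NIH (2.2). Follow-up scans may be done elsewhere, but 3.4 and 3.6 have the images sent to NIH for tumor measurement. Outside follow-up therefore does not guarantee separate readers.

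No section supplies the missing separation.

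**Is there time to record FMISO first?** Inputs: post-TACE FMISO at 24 to 72 hours, that is 1 to 3 days (Précis, 3.4); follow-up CT/MRI at 4 to 6 weeks, that is 28 to 42 days (3.1.3, 6.2.3). Both are taken as counted from TACE.

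- Shortest gap: 28 − 3 = 25 days.
- Longest gap: 42 − 1 = 41 days.

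The FMISO regions can be drawn before the first follow-up scan exists.

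**What would an overlap figure be read against?** Let *s* be the share of the whole tumor volume that the FMISO region occupies, and *o* the share of the progression site inside that region. If progression fell at random within the tumor, the expected value of *o* would equal *s*. A large *o* means little if *s* is also large, so both must be reported, with the same margin applied to each.

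**The case against.** The strongest reply is that this is a small proof-of-concept study for which section 8 sets aside power and significance. The primary objective in 1.1.1 is feasibility and description of hypoxia patterns just after TACE, and no go/no-go decision uses the match. The feasibility grade and the early decisions in 3.2 and 3.7 also make a wholly retrospective FMISO read unlikely. All of that stands, and it limits the scope of the point. It does not supply a recorded FMISO location.

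Three stronger readings are tempting and are not supported:

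- **That one reader certainly sees and knows everything.** The documents never say who reads what. Knowledge of the site is an inference from selecting progressed tumors and reading fused images with no masking stated. Section 7.5.1 says "Any adverse event, toxicity, and imaging evaluations will be discussed as a group", but that sits in the data and safety monitoring plan and describes team meetings, not how overlap is scored.
- **That the bias can be sized.** One could assume a tumor and a focus, vary the distance accepted as a match, and watch chance agreement rise. That would show the effect of an undefined tolerance, which a masked reader without a rule would share. It would not measure the effect of knowing the site. It would also rest on lesion sizes the documents do not give, and it would not cover growth beyond the original edge, which 3.3 also counts as progression.
- **That the feasibility result is compromised.** The 3.7 rule and the objective in 1.1.1 use uptake, not its match with progression.

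**Conclusion.** The point holds for the correlation aim. As written, the plan permits a reading informed by the outcome, and no safeguard in the documents closes that route. The likely direction is toward the hypothesis. The documents give no basis for a numerical size. Section 3.1 plans 15 patients to yield at least 10 evaluable, and only tumors that progress contribute, so a few discretionary calls could shape what is reported.

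The conclusion assumes that the steps in 3.3 are carried out in the order given and that no unstated masking is in place. It is a change the sponsor should make, not a flaw that undermines the study.

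**What to change.** In section 3.3, set the reading order:

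1. Using only the FMISO PET-CT and the pre-TACE imaging, assign the uptake category and contour the regions of increased and of decreased uptake in every treated tumor. Save them with a date before any follow-up CT or MRI is opened.
2. Mark the progression site on the follow-up CT or MRI without PET displayed.
3. Then fuse. For each locked region, report descriptively the share of the progression site inside it, using one pre-stated margin to allow for registration error. Beside it give the share of the whole tumor that the locked region occupies with the same margin, as the chance reference.

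Contouring both kinds of region keeps the increased-or-decreased question that 3.3 asks. Contouring every treated tumor also leaves a record for tumors that do not progress. The documents give no registration error, so the sponsor must choose and state the margin. The chance reference applies to progression within the original tumor outline; growth outside it should be described separately.

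The cost is protocol wording, dated saved contours and extra contouring time per lesion. The reader, images and software can stay the same.

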8 STATISTICAL CONSIDERATIONS

The study is a proof of concept protocol. It aims to determine the feasibility of acute hypoxia imaging of the liver following TACE. Power and significance calculations are not applicable to this small sample feasibility study.

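### The FMISO-progression reading in Section 3.3 ignores the focal/diffuse label and has no reference for overlap expected without a link, so tumors avid throughout read as co-located whatever the biology

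*Combined protocol and SAP*

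**What the plan says.** Section 3.3 (Image Analysis) has two relevant steps. For feasibility, treated tumors are classed as absent, background or increased against liver, and: "Lesions demonstrating any increased activity compared to background liver will be further characterized as diffusely or focally increased activity". Then, for the link with progression: "Individual liver tumors which demonstrate progression defined by increased size and/or enhancement will be evaluated for geographic FMISO uptake correlation". The progression CT or MRI is registered automatically to the FMISO PET-CT, "to determine whether qualitatively increased or decreased FMISO uptake is observed in spatial relation to tumor progression". SUV or tumor-to-serum quantification follows only where increased activity coincides with progression.

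Two other sections describe the same analysis differently. Section 1.2.3 (Rationale) says image fusion will give the "degree of correlation between focal hypoxia and site(s) of progression". Section 6.1 (Data Collection) speaks of "characterization of degree of overlap between documented tumor progression and acute post-treatment hypoxia", with no restriction to focal uptake.

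On timing, the post-TACE PET is done at 24 to 72 hours (Section 3.4). The follow-up CT and MRI come every 4 to 6 weeks, and the interval may widen to 3 months once disease is stable (Section 3.1.3). Section 8 adds no analysis plan; it says only that "Power and significance calculations are not applicable to this small sample feasibility study".

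**The concern.** The reading is meant to show whether progression arises where the tumor was hypoxic after embolization. That needs a contrast within the tumor between avid and non-avid tissue. A tumor avid throughout has no such contrast: progression anywhere inside the avid volume sits in increased uptake. A focal tumor does have the contrast, but finding progression inside the focus means little until it is compared with how much of the tumor the focus fills.

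Section 3.3 collects the label that separates the two cases and then reads all progressing tumors the same way. It does not measure the avid share of the tumor, and no section gives a comparator.

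The reading also depends on aligning a PET taken within days of TACE with a scan taken weeks to months later, when the tumor may have changed size and shape. No section gives a measure of alignment error or a tolerance for it.

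At stake is whether the description of co-location can be interpreted. Section 1.2.3 presents early detection of residual hypoxia as a possible guide to combined treatment, so a spatial link that merely reflects diffuse uptake, or a focal link lost to misalignment, would mislead that next step.

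**Working it through.** **What there is to reproduce.** The documents give no overlap figure, threshold or sample-size calculation for this analysis. Section 3.1 gives only 15 patients "enrolled to yield a minimum of ten evaluable patients".

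**Assumptions.** The documents give no avid share, proportion of diffuse tumors, lesion size or registration error, so all are assumed below and varied. Ten progressing tumors is also an assumption: ten is the minimum number of evaluable patients, not all need progress, and one patient may have several tumors.

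**Step 1: overlap expected without a link.** Suppose progression is equally likely anywhere within the tumor volume seen on PET. If a share f of that volume is avid, the expected co-location is f. For a tumor avid throughout, f = 1. If a proportion q of tumors is avid throughout and the rest are focal with share f, the expected co-location rate is

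m = q + (1 − q) × f

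For q = 0.5 and f = 0.25: 0.5 + 0.5 × 0.25 = 0.625.

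| Avid throughout (q) | f = 0.10 | f = 0.25 | f = 0.40 |
|---|---|---|---|
| 0% | 10% | 25% | 40% |
| 30% | 37% | 47.5% | 58% |
| 50% | 55% | 62.5% | 70% |
| 70% | 73% | 77.5% | 82% |

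**Step 2: what one result would mean.** Take 7 or more of 10 tumors reading as co-located, with no true link, f = 0.25, and tumors independent. If each tumor is avid throughout with probability q, the binomial tail P(X ≥ 7; 10, m) is 0.4%, 13%, 45% and 83% for q = 0, 30%, 50% and 70%. If exactly 3, 5 or 7 of the ten are avid throughout, the focal tumors must supply 4 of 7, 2 of 5 or 0 of 3. With chance 0.25 each, that is 7%, 37% and 100%. For example, 2 or more of 5: 1 − 0.75^5 − 5 × 0.25 × 0.75^4 = 1 − 0.237 − 0.396 = 0.367. On either reckoning, the same result ranges from near-conclusive to empty, depending on a quantity the reading does not use.

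**Step 3: registration error, loss of overlap.** Two equal spheres of radius r at offset d overlap by 1 − 3d/(4r) + d³/(16r³).

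- 20 mm focus and progression site (r = 10): 63% at 5 mm, 31% at 10 mm, 9% at 15 mm.
- 10 mm focus and site (r = 5): 31% at 5 mm, 0% at 10 mm.

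**Step 4: registration error, misreadings.** This is a simulation with 400,000 draws per setting: a spherical focus placed at random in a spherical tumor, progression taken as a point, and a Gaussian three-dimensional shift with RMS error of 5, 10 or 15 mm.

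| Focus / tumor diameter | True match still read as match | True mismatch read as match |
|---|---|---|
| 15 / 30 mm | 56%, 26%, 12% | 5.5%, 6.9%, 5.3% |
| 20 / 50 mm | 67%, 39%, 21% | 2.2%, 3.7%, 3.9% |
| 25 / 50 mm | 73%, 49%, 30% | 3.7%, 6.2%, 7.0% |

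In the 15/30 mm case the focus fills (7.5/15)³ = 12.5% of the tumor. With no link, the co-location rate at 5 mm error is 0.125 × 0.561 + 0.875 × 0.055 = 11.8%, against 12.5% with perfect registration. At 10 mm it is 0.125 × 0.256 + 0.875 × 0.069 = 9.2%. Registration error therefore does not create an apparent link here. It removes true ones, most of all for small foci.

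**The case against.** The best reply is that this is a descriptive proof-of-concept study whose one stated objective (Section 1.1.1) is feasibility and the pattern of hypoxia. The progression link appears in the design and rationale, not there. Section 1.2.3 already names focal hypoxia, and Section 3.3 already records focal or diffuse. So the restriction and the data exist, and only the wording needs aligning. Much of this stands: the primary reading is unaffected, and no hypothesis test is called for. What remains is that Section 3.3, the operative text, does not apply the restriction, and even for focal lesions no section supplies the reference that gives an overlap its meaning.

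A reader might infer more than the documents support:

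- *That a diffusely avid tumor matches wherever it progresses.* This holds only inside the avid volume. The diffuse label is relative to liver and does not mean uniform uptake to the margin. Section 3.3 counts increased size as progression, so growth may lie outside the volume seen on PET and read as a mismatch.
- *That half the tumors match by construction if half are diffuse.* This needs complete coverage. At 80% coverage, five diffuse tumors give 5 × 0.8 = 4 expected matches, and all five match with probability 0.8^5 = 0.33.
- *That misregistration will be reported as a hypoxia-progression link.* The protocol says registration is automatic; it does not say that fused images go unreviewed. Steps 3 and 4 show the error working mainly toward no association.
- *That the study will publish an inflated match count.* No section defines a tally. The percentages in Step 1 show how co-location would read if summarized, not a promised output.

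**Conclusion.** The concern holds for the progression-correlation aim in Section 1.2.3. The reading in Section 3.3 cannot separate a spatial link from extensive uptake, because it neither uses the focal/diffuse label nor sets observed overlap against the avid share of the tumor.

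The size depends on quantities that the documents do not give. With foci covering 25% of the tumor, co-location expected without a link rises from 25% to 77.5% as the proportion of tumors avid throughout goes from 0% to 70%. This assumes that progression falls inside the tumor volume seen on PET, at a place unrelated to uptake. It does not cover growth beyond that margin.

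Unmeasured registration error is a second, separate weakness, acting mostly in the opposite direction: it would hide true focal matches, especially for small foci. Neither weakness touches the feasibility classification of uptake. The change is worth making because it is cheap and because, without it, the spatial result would be hard to interpret either way.

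**What to change.** 1. Make Sections 1.2.3, 3.3 and 6.1 describe one analysis.
2. Report focal and diffuse lesions separately, and base any statement on focal hypoxia and progression on focal lesions only. List diffuse lesions as uninformative on location.
3. For progression inside the tumor volume seen on PET, report for each lesion the share of the progression site with FMISO above liver beside the share of the whole treated tumor above liver. Use one above-liver threshold fixed in advance; Section 3.2 expects high activity in normal liver, so it must be stated.
4. List progression beyond the original tumor margin separately, since the whole-tumor share is not a valid reference there.
5. For each fused pair, record the residual registration error at anatomical landmarks. Call a mismatch only where the separation exceeds that error. Call a match only where the sites overlap and the focus is large relative to that error. Otherwise call the lesion indeterminate. Do not require separation to exceed the error for a match, because a true match has almost none and could then never be called.

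The cost is extra workstation measurement, including PET segmentation at the chosen threshold, on images that are already to be fused. No further patients or scans are needed. Fewer lesions will contribute to the localization result, which should be accepted and stated.
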